6. GENERAL STATISTICAL CONSIDERATIONS

6.1. General Principles

All continuous variables will be summarized using the following descriptive statistics: n (non-missing sample size), mean, standard deviation, median, minimum and maximum, unless otherwise specified. The frequency and percentage of observed levels will be reported for all categorical measures; denominators for percentages will be defined for each analysis.

Listings will be provided for all data. Sort order will be specified on each listing shell in Appendix 3.

Summary tables will be structured with a column for each treatment group (2.5 mcg ZPIV, 5 mcg ZPIV, Placebo) and for all subjects for safety summaries.

All tables will be annotated with the total population size relevant to that table/group, including any missing observations.

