[Implementation note: N = Number of subjects in the Safety population with specified baseline flavivirus immune status]

Table 39: Overall Summary of Adverse Events – Baseline ZIKV Seropositive and DENV Seropositive Subjects

[Implementation note: N = Number of subjects in the Safety population with specified baseline flavivirus immune status]

Table 40: Overall Summary of Adverse Events – Baseline ZIKV Seropositive and DENV Seronegative Subjects

[Implementation note: N = Number of subjects in the Safety population with specified baseline flavivirus immune status]

Table 41: Overall Summary of Adverse Events – Baseline ZIKV Seronegative and DENV Seropositive Subjects

[Implementation note: N = Number of subjects in the Safety population with specified baseline flavivirus immune status]

Table 42: Overall Summary of Adverse Events – Baseline ZIKV Seronegative and DENV Seronegative Subjects

[Implementation note: N = Number of subjects in the Safety population with specified baseline flavivirus immune status]

14.3.1.1 Solicited Adverse Events**Table 43: Comparison of the Frequency, Type and Duration of Vaccine-Related Grade 3 Local, Systemic or Laboratory AEs and Grade 2 or Greater Local or Systemic Reactogenicity Through Day 8 Post Vaccination**

Post Dose Number	AE Type	Symptom/Lab AE	2.5 mcg ZPIV		5 mcg ZPIV		Placebo		p-value		
			n	Median Duration (Days)	n	Median Duration (Days)	n	Median Duration (Days)	^a Frequency	^b Duration	
All Subjects											
Post Dose 1	Number of Subjects in the Safety Population Who Received the Specified Dose			x	N/A	x	N/A	x	N/A	N/A	
	Vaccine related Grade 3 local, systemic or laboratory AE	[Event 1]	x	x.x	x	x.x	x	x.x	x.XXX	x.XXX	
		[Event 2]							x.XXX	x.XXX	
		[Event 3]							x.XXX	x.XXX	
		Etc.							x.XXX	x.XXX	
	*Grade 2 or greater local or systemic reactogenicity	[Event 1]							x.XXX	x.XXX	
		[Event 2]							x.XXX	x.XXX	
		[Event 3]							x.XXX	x.XXX	
		Etc.							x.XXX	x.XXX	
Repeat Post Dose 1 for:											
Baseline ZIKV Seropositive											
Baseline ZIKV Seronegative											
Baseline ZIKV Seropositive and DENV Seropositive											
Baseline ZIKV Seropositive and DENV Seronegative											
Baseline ZIKV Seronegative and DENV Seropositive											
Baseline ZIKV Seronegative and DENV Seronegative											
All Subjects											
Post Dose 2	Number of Subjects in the Safety Population Who Received the Specified Dose			x	N/A	x	N/A	x	N/A	N/A	
		[Event 1]	x	x.x	x	x.x	x	x.x	x.XXX	x.XXX	

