Table 138: Number and Percentage of Subjects Reporting Serious Adverse Events Related to Study Treatment by MedDRA System Organ Class, Preferred Term, Treatment Group, and Baseline Flavivirus Immune Status

Table with similar format to Table 111:

Table 139: Duration (Days) of Serious Adverse Events Related to Study Treatment by MedDRA System Organ Class, Preferred Term, Treatment Group, and Baseline Flavivirus Immune Status

Table 140: Summary of AFI/ARI Events Reported Through 12 Months Post Final Vaccination by Treatment Group – All Subjects

[Implementation note: This table can include any subjects who did not have a baseline flavivirus status observed.]

Infection Confirmation Status	2.5 mcg ZPIV (N=X)				5 mcg ZPIV (N=X)				Placebo (N=X)				All Subjects (N=X)			
	Number of Events	Number of Subjects	% of Subjects	95% CI	Number of Events	Number of Subjects	% of Subjects	95% CI	Number of Events	Number of Subjects	% of Subjects	95% CI	Number of Events	Number of Subjects	% of Subjects	95% CI
All Events	x	x	xx	x.x, x.x	x	x	xx	x.x, x.x	x	x	xx	x.x, x.x	x	x	xx	x.x, x.x
Events Requiring Concomitant Medication																
Events Requiring Medical Treatment ^a																

N = Number of subjects in the Safety population
% = percentage of subjects reporting at least one AFI/ARI event out of total number of subjects in the Safety population in the group
95% CI is calculated using the Clopper-Pearson methodology for a binomial distribution.
This table includes subjects who only received dose 1.
^aIncludes hospitalization or other medical care

Tables with similar format:

Table 141: Summary of AFI/ARI Events Reported Through 12 Months Post Final Vaccination by Treatment Group – Baseline ZIKV Seropositive Subjects

[Implementation note: If no subjects are flavivirus positive at baseline, replace this table with the following note: 'Table not generated since no positive arbovirus results were reported for ZIKV or DENV.]

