Table 142: Summary of AFI/ARI Events Reported Through 12 Months Post Final Vaccination by Treatment Group – Baseline ZIKV Seronegative Subjects**Table 143: Summary of AFI/ARI Events Reported Through 12 Months Post Final Vaccination by Treatment Group – Baseline ZIKV Seropositive and DENV Seropositive Subjects****Table 144: Summary of AFI/ARI Events Reported Through 12 Months Post Final Vaccination by Treatment Group – Baseline ZIKV Seropositive and DENV Seronegative Subjects****Table 145: Summary of AFI/ARI Events Reported Through 12 Months Post Final Vaccination by Treatment Group – Baseline ZIKV Seronegative and DENV Seropositive Subjects**

Table 146: Summary of AFI/ARI Events Reported Through 12 Months Post Final Vaccination by Treatment Group – Baseline ZIKV Seronegative and DENV Seronegative Subjects

Table 147: Number of Laboratory Confirmed ZIKV or DENV Infections Overall and by Confirmation Method – All Subjects

[Implementation note: This table can include any subjects who did not have a baseline flavivirus status observed.]

Infection Confirmation Status	2.5 mcg ZPIV (N=X)				5 mcg ZPIV (N=X)				Placebo (N=X)				All Subjects (N=X)			
	Number of Events	Number of Subjects	% of Subjects	95% CI	Number of Events	Number of Subjects	% of Subjects	95% CI	Number of Events	Number of Subjects	% of Subjects	95% CI	Number of Events	Number of Subjects	% of Subjects	95% CI
Positive by PCR ^a	X	X	XX	X.X, X.X	X	X	XX	X.X, X.X	X	X	XX	X.X, X.X	X	X	XX	X.X, X.X
Positive by 4-Fold Titer Rise ^b																
Any Positive Confirmation ^{a,b}																
Negative Lab Confirmation																

N = Number of subjects in the Safety Population

% = percentage of subjects reporting at least one AFI/ARI event/total number of subjects in the Safety population in the group

95% CI is calculated using the Clopper-Pearson methodology for a binomial distribution.

This table includes subjects who only received dose 1.

^a PCR confirmation includes a positive PCR result for at least one of ZIKV (blood or urine) or DENV.^b 4-fold rise in either ZIKV or DENV neutralization titers after the ARI/AFI illness visit compared to before the illness visit.^c Includes hospitalization or other medical care

Tables with similar format:

Table 148: Number of Laboratory Confirmed ZIKV or DENV Infections Overall and by Confirmation Method – Baseline ZIKV Seropositive Subjects

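### The percentage footnote on SAP Table 147 counts subjects with any AFI/ARI, not subjects with a confirmed infection, so its literal reading puts the same attack rate in every confirmation row.

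*SAP*

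**What the plan says.** SAP Appendix 1, Table 147 is titled "Number of Laboratory Confirmed ZIKV or DENV Infections Overall and by Confirmation Method". Each treatment column holds a number of events, a number of subjects, a percentage of subjects and a 95% CI. The rows are the confirmation results: positive by PCR, positive by 4-fold rise, any positive, and negative.

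Two footnotes define the percentage: "N = Number of subjects in the Safety Population" and, for the % sign, "percentage of subjects reporting at least one AFI/ARI event/total number of subjects in the Safety population in the group". The interval is Clopper-Pearson. Tables 148-153 repeat the shell for the serostatus subgroups and are listed only as having a similar format, with no definitions of their own.

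Table 140, which summarises AFI/ARI events, has nearly the same footnote: "percentage of subjects reporting at least one AFI/ARI event out of total number of subjects in the Safety population in the group". Its serostatus versions, Tables 141-146, likewise carry no note on N. By contrast, Tables 37-42 carry the instruction "N = Number of subjects in the Safety population with specified baseline flavivirus immune status".

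SAP Section 6.1 says that "denominators for percentages will be defined for each analysis". SAP Section 9.9 describes these tables in prose but gives no numerator or denominator.

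**The concern.** The numerator in the Table 147 footnote is anyone with at least one AFI/ARI. It does not depend on the row, although the rows are the whole content of the table. A percentage built to that definition is the AFI/ARI attack rate, printed four times under four infection labels, with an interval to match.

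Table 147 and its subgroup versions present confirmed infections by product received and prior flavivirus immunity, which is what the exploratory objective asks to have estimated. If the footnote is programmed, the printed infection percentages are wrong. If a programmer ignores it and divides the row count by N, the footnote misdescribes what is printed. The shell needs correcting in either case.

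**Working it through.** **Is there a figure to reproduce?** No. The documents state no rate, count or precision for these tables. The check compares definitions and then illustrates with assumed counts.

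**Where the footnote comes from.** The Table 140 wording fits that table's all-events row. Table 147 repeats it with almost no change. Table 147 also carries a footnote c, on hospitalization and other medical care, that no row uses. Both features suggest text carried over from a neighbouring shell. Table 168, in the same series, does define a denominator tied to the confirmation result, so row-specific definitions were within the authors' practice.

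**Inputs.** Group sizes come from SAP Section 4.4.3: N = 35 (2.5 mcg), N = 45 (5 mcg) and 5 + 5 = 10 pooled placebo. Assumed: A = 5 to 15 subjects with AFI/ARI per vaccine group, of whom C = 0 to 5 are confirmed, with each AFI/ARI subject either confirmed or negative.

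**Formulas.** Footnote as written: A/N in every row. Row-specific: C/N for any positive and (A − C)/N for negative.

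**Example, 2.5 mcg, A = 10, C = 2 (exact 95% CI):**

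| Row | Footnote as written | Row-specific numerator |
|---|---|---|
| Any positive | 10/35 = 28.6% (14.6 to 46.3) | 2/35 = 5.7% (0.7 to 19.2) |
| Negative | 10/35 = 28.6% (14.6 to 46.3) | 8/35 = 22.9% (10.4 to 40.1) |

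**Range for the any-positive row:**
- N = 35: 5/35 to 15/35 = 14.3% to 42.9% as written, against 0/35 to 5/35 = 0% to 14.3%.
- N = 45: 5/45 to 15/45 = 11.1% to 33.3% as written, against 0/45 to 5/45 = 0% to 11.1%.
- Placebo, N = 10, with A = 5 and C = 1: 50.0% as written, against 10.0%.

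A row is right by coincidence when every AFI/ARI subject falls in it, for example the negative row when nobody is confirmed.

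**Serostatus tables.** Take a 2.5 mcg stratum of s subjects with 4 AFI/ARI and 1 confirmed:

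| s | Footnote numerator, whole-arm N | Row-specific numerator, whole-arm N | Footnote numerator, stratum N | Row-specific numerator, stratum N |
|---|---|---|---|---|
| 5 | 4/35 = 11.4% | 1/35 = 2.9% | 4/5 = 80.0% | 1/5 = 20.0% |
| 10 | 11.4% | 2.9% | 4/10 = 40.0% | 1/10 = 10.0% |
| 20 | 11.4% | 2.9% | 4/20 = 20.0% | 1/20 = 5.0% |
| 30 | 11.4% | 2.9% | 4/30 = 13.3% | 1/30 = 3.3% |

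With numerator and N both taken at their most literal (second column), the result is below the intended rate (last column) for s = 5 and above it for s = 10, 20 and 30. The direction of error is not fixed.

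**The case against.** The best defence is that the footnote is generic and the row label supplies the condition. Table 140 uses the same wording over rows for events needing medication or medical treatment. Table 154 defines its percentage as events over total events, which without its row labels is 100% throughout. Section 9.9 describes Tables 140-144 as counts and percentages of subjects with an event, and Tables 147-151 as the same by confirmation method. In Table 147 the row-specific count sits beside the percentage. A sensible programmer would probably divide that count by N.

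Most of this stands as a forecast of what will be programmed. It does not make the definition correct. Section 6.1 leaves denominators to each analysis, so the footnote is the only formula given. Section 9.9 is also an uncertain guide, because it assigns the total of confirmed infections to Tables 154-158, whereas the shell with that title is Table 147.

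On the strata, the defence is stronger. Each title restricts the table to a serostatus group, and Section 6.1 requires each table to show the population size that applies to it. A stratum N is the natural reading, and the missing note leaves only an ambiguity.

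Three stronger readings are tempting, and the documents do not support them:
- *The tables fail to report infections.* Event and subject counts are separate columns that do not depend on the footnote. Exploratory endpoint 2 asks for the number and severity of infections, and the number is intact.
- *Every serostatus rate is wrong, and smaller strata look safer.* That needs N to be the whole arm, which the titles and Section 6.1 argue against. A dilution that is worse in smaller strata also needs the numerator already corrected; with both parts literal the error can go either way.
- *Exploratory endpoint 1 requires AFI/ARI subjects as the denominator.* Its wording does not fix a denominator.

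**Conclusion.** The concern holds for the numerator. As written, the Table 147 footnote defines the AFI/ARI attack rate for all four confirmation rows, and Tables 148-153 inherit it. With 10 AFI/ARI subjects and 2 confirmed among 35, the any-positive row would show 28.6% instead of 5.7%. The size rests wholly on assumed counts; only the group sizes come from the SAP. The Safety-population denominator suits an incidence objective and is not at fault.

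The missing stratum note on Tables 141-146 and 148-153 is an ambiguity worth closing. It does not establish that those tables would use the wrong N. The endpoint is exploratory and the infection counts are safe, so this is a shell correction to make before the tables are programmed.

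**What to change.** 1. Table 147, carried to Tables 148-153: replace the percentage footnote with *% = subjects with at least one AFI/ARI event meeting the row's confirmation status / N*. Keep N as the Safety population in the column, and delete the unused footnote c.
2. Tables 141-146 and 148-153: add a note that N counts Safety-population subjects in the treatment group with the baseline serostatus named in the title, following Tables 37-42.
3. Optional: a line giving confirmed subjects as a share of subjects with AFI/ARI.

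The cost is one rewritten footnote and one standard note on twelve shells (6 + 6). No data, design or analysis method changes.

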### **Exploratory Endpoints**

1. Number and proportion of subjects who develop an acute febrile illness (AFI) or an acute rash illness (ARI) who have evidence of acute ZIKV or DENV infection within 14 days of symptom onset. This endpoint will be analyzed for all subjects overall, and by treatment group and pre-vaccination flavivirus immune status.
2. Number and severity of laboratory confirmed ZIKV and DENV infections during the study, overall, by treatment group, and pre-vaccination immune status, where severity is described by:
  - Duration of symptoms
  - Grade of symptoms (mild, moderate, severe)
  - Use of concomitant medications
  - Need for hospitalization or other medical care.

Laboratory confirmation will be made by AFI or ARI with either: 1) evidence of acute ZIKV or DENV infection within 14 days of symptom onset or 2) a 4 fold rise in DENV or ZIKV neutralization titers between samples collected at the last visit prior to and at the first visit following the AFI/ARI illness visit, where available.

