3. STUDY OBJECTIVES AND ENDPOINTS

3.1. Study Objectives

Primary Objectives:

1. Assess the safety and reactogenicity of a homologous prime boost regimen of ZPIV given at two different dose levels in a dose de-escalation format in healthy adult subjects who live in Puerto Rico, a flavivirus endemic area.
2. Compare the safety and reactogenicity profile of ZPIV after each vaccination, between dosage groups, and by pre-vaccination flavivirus immune status.

Secondary Objectives:

1. Assess the humoral immune response to a homologous prime-boost regimen of ZPIV after each dose of vaccine as determined by kinetics of the immune responses, seroconversion rates, and Geometric Mean Titers (GMT) overall, and compare results between dosage groups and by pre-vaccination flavivirus immune status.
2. Assess the durability of the humoral immune response to ZPIV at 6, 12, 18, and 24 months after the second vaccine administration overall, and compare results between dosage groups and by pre-vaccination flavivirus immune status.

Exploratory Objectives

1. Estimate the incidence of ZIKV and DENV infections between Visit 00 and the subject's last visit and describe the clinical presentation including disease severity overall, by dosage group, product received, and pre-vaccination flavivirus immune status.

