Baseline DENV and ZIKV serostatus will be determined via IgM antibody and IgG ELISA assays, with subject results reported as either 'positive' or 'negative'. If a subject has a positive ZIKV result from either the IgM or IgG ELISA assays, they will be considered ZIKV seropositive at baseline. If a subject has inconclusive results for their baseline flavivirus immune status, they will not be included in analyses stratified by baseline flavivirus immune status but will be included in analyses of all subjects.

Post-Baseline Seropositivity

Seropositivity post-baseline is defined as a titer ≥ 10 and ≥ 100 for ZIKV MN50 and a titer ≥ 200 and ≥ 600 for ZIKV ELISA.

Seroconversion

Seroconversion for ZIKV MN50 titers and ZIKV ELISA titers is defined as ≥ 4 -fold rise from baseline.

Acute Febrile Illness and Acute Rash Illness

Acute febrile illness (AFI) is defined as grade 1 or higher fever on at least 2 consecutive days accompanied by any of the following: new rash not limited to vaccination site, arthralgia, or nonpurulent conjunctivitis. Acute rash illness (ARI) is defined as any new rash not limited to vaccination site.

Laboratory Confirmation of ZIKV or DENV Infection Among Those with AFI or ARI

Among subjects with AFI or ARI, laboratory confirmation of ZIKV or DENV infection will be made by either 1) evidence of acute ZIKV and DENV infection within 14 days of symptom onset (confirmed via PCR) or 2) a 4-fold rise in DENV or ZIKV neutralization titers between samples collected at the last visit prior to and at the first visit following the AFI/ARI illness visit, where available.

Consideration of ZIKV Microneutralization Assay Results in Analysis

The lower limit of quantitation (LLOQ) for ZIKV microneutralization assay results is 10. Any values less than the LLOQ will be assigned a value of 5 by the lab. This imputed value will be used for the purpose of calculating summary statistics such GMT and will be displayed in listings of immunogenicity data. If a subject has a baseline titer below the LLOQ (reported as 5), then they will be considered seroconverted if the post-baseline titer is at least 20 (at least a 4-fold rise). Similarly, a subject with a baseline ZIKV MN50 below the LLOQ will be considered seropositive if the post-baseline titer is at least 10 or 100, as applicable.

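### No planned summary table reports ZIKV and DENV infections separately, and the first arm of the confirmation rule is worded inconsistently

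*SAP*

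**What the plan says.** The objective, in Protocol 3.1.3 and SAP 3.1, begins: "Estimate the incidence of ZIKV and DENV infections between Visit 00". It runs to the last visit and also covers clinical presentation and severity, by dosage group, product received and baseline serostatus. Protocol 11.4.4 gives the viruses separate severity bases: four items for ZIKV, and for DENV those items as set out in the 1997 and 2009 WHO guidelines.

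SAP 3.3 gives two routes to laboratory confirmation in a subject with AFI or ARI. The first is "evidence of acute ZIKV and DENV infection within 14 days of symptom onset", to be confirmed by PCR. The second is "a 4-fold rise in DENV or ZIKV neutralization titers between samples collected at the last visit prior to" the illness and at the first visit after it. The Protocol synopsis words the rule differently: "evidence of acute ZIKV or DENV infection within 14 days of symptom onset or 2) a 4 fold rise in DENV or ZIKV neutralization titers".

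The shells use a third form. Footnote a to Table 147 reads "PCR confirmation includes a positive PCR result for at least one of ZIKV (blood or urine) or DENV", and footnote b reads "4-fold rise in either ZIKV or DENV neutralization titers after the ARI/AFI illness visit compared to before the illness visit". The rows are PCR positive, titer positive, any positive and negative. SAP 9.9 breaks the infection results down by treatment group, baseline serostatus and confirmation method, and describes the first route as a positive arbovirus PCR without naming a virus.

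Listing 12 gives, for each illness, separate columns for ZIKV PCR in blood, ZIKV PCR in urine, DENV PCR, CHIKV PCR, ZIKV 4-fold rise and DENV 4-fold rise.

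**The concern.** This is a ZIKV vaccine studied where both viruses are expected to circulate. A pooled count mixes the infection the vaccine targets with one it does not. If the summaries never separate them, the reader of the clinical study report gets neither incidence with its interval, and the DENV severity basis in Protocol 11.4.4 has no table to appear in.

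The inconsistent case rule is a second problem. Three definitions join the viruses with *and*, other places use *or*, and one names no virus. A programmer could follow any of them in good faith and obtain different counts of confirmed cases.

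**Working it through.** No sample size or event figure in the documents bears on this point. The check is textual, followed by two illustrations with assumed counts and rates.

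**1. The shells.** Tables 147-153, 154-160, 168-174 and 182-188 are four sets of seven (all subjects plus six serostatus groups), so 4 × 7 = 28 tables. None has a row or column for a single virus. (Numbers follow the shells in SAP Appendix 1; SAP 9.9 describes the 147 and 154 series the other way round.)

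**2. The case rule, side by side.**

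| Place | First arm | Titer arm |
|---|---|---|
| Protocol synopsis, exploratory endpoint 2 | ZIKV *or* DENV | either virus |
| Protocol 3.2.3, endpoint 2 | ZIKV *and* DENV | either virus |
| Protocol 11.4.4 | ZIKV *or* DENV, RNA or other evidence | not restated |
| SAP 3.2, endpoint 2 | ZIKV *and* DENV | either virus |
| SAP 3.3 | heading and lead-in *or*; the rule itself *and*, by PCR | either virus |
| SAP 9.9 | arbovirus PCR, virus not named | either virus |
| Footnotes to Tables 147, 154, 182 | at least one of the two | either virus |

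The illness-visit panel includes CHIKV (Protocol 7.1.3 and Appendix A). Taken alone, the SAP 9.9 wording could therefore count a CHIKV-only positive.

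**3. What pooling hides (counts assumed).** Take six confirmed cases in the 90 planned subjects, no dual infections, and Clopper-Pearson intervals as in the shells. The pooled row is 6/90 = 6.7% (2.5 to 13.9) in every case.

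| Split | One virus | Other virus |
|---|---|---|
| 0 / 6 | 0% (0 to 4.0) | 6.7% (2.5 to 13.9) |
| 1 / 5 | 1.1% (0.0 to 6.0) | 5.6% (1.8 to 12.5) |
| 3 / 3 | 3.3% (0.7 to 9.4) | 3.3% (0.7 to 9.4) |

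**4. What *and* does to the PCR arm (rates assumed).** Suppose each virus is PCR-positive in a proportion p of subjects, independently. *Or* confirms 1 − (1 − p)²; *and* confirms p².

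| p | *or* | expected in 90 | *and* | expected in 90 |
|---|---|---|---|---|
| 1% | 1.99% | 1.8 | 0.01% | 0.01 |
| 5% | 9.75% | 8.8 | 0.25% | 0.2 |
| 10% | 19.0% | 17.1 | 1.0% | 0.9 |

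These figures cover PCR only. The titer arm accepts either virus wherever it is stated, so cases with a 4-fold rise remain confirmed under any reading.

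**5. The titer arm and the vaccine response.** SAP 3.3 defines seroconversion as a 4-fold rise in ZIKV MN50, the same size of rise that confirms infection. SAP 4.5 places samples on Days 1, 15, 29 and 43, with those of Days 1 and 29 taken before vaccination. A new rash between Days 1 and 15, or between Days 29 and 43, is therefore flanked by samples that span a dose. In a ZPIV recipient below the quantitation limit at baseline (recorded as 5), a Day 15 titer of 20 is a rise of 20/5 = 4 and meets both definitions. The pooled row would not show that such a case rests on a ZIKV titer rise.

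**The case against.** The strongest reply is that nothing is lost. Listing 12 holds PCR and titer results by virus for each illness, Listing 8 holds both MN50 titers by subject, and counts by virus and group can be tallied from them. This stands against a stronger inference a reader might draw, that the trial cannot report the incidence of either virus: the gap is in the planned summaries and the missing attribution rule. But a listing has no denominators, percentages or intervals, and nothing says how to classify an event with rises in both titers.

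A reader might also infer that the plan requires both viruses by PCR. The documents do not support that as the settled rule. The synopsis, Protocol 11.4.4, the table footnotes and the heading and lead-in of SAP 3.3 all point to *or*, and the objective itself uses *and* distributively. The *and* is probably a drafting slip, but it still sits in three definitions.

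It is also fair that the endpoint is exploratory, that one stated purpose (Protocol 11.1) is preliminary data on natural flavivirus infections in general, and that rows by virus in serostatus subgroups would often be empty. These points limit the priority and the number of tables to change. They do not remove the mismatch with the objective.

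**Conclusion.** The point holds in two limited parts. First, all 28 infection shells and SAP 9.9 pool the viruses, so no planned summary answers exploratory objective 1 by virus or carries the separate DENV severity basis. Second, the first arm of the case rule contradicts itself across the documents. Read literally, *and* would drop single-virus cases confirmed by PCR only. A reader might infer that it would leave no confirmed cases at all; that does not follow, because the titer arm still confirms.

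Nor do the documents support describing pooling as diluting an estimated vaccine effect. Protocol 11.1 states no formal hypothesis, about 10 placebo subjects are planned, and the infection-count shells hold only counts, percentages and intervals.

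The real size cannot be stated, because the documents give no expected number of infections. The figures above rest on assumed counts and rates, no dual infections in the splits, and independent PCR results. This is an inexpensive improvement to the tables plus the correction of an internal contradiction, on an exploratory endpoint.

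**What to change.** 1. Write ZIKV *or* DENV in the first arm of the rule in Protocol 3.2.3 and SAP 3.2 and 3.3, and name the two viruses in SAP 9.9 so that a CHIKV-only positive cannot count.
2. In SAP 3.3 define ZIKV-confirmed, DENV-confirmed and both/indeterminate, and state where an event with rises in both titers belongs.
3. Flag ZIKV titer rises whose flanking samples span a study vaccination. Without the flag, a row for ZIKV by titer rise could mix infection with vaccine response.
4. Add ZIKV, DENV, both/indeterminate and Any rows at least to the all-subject Tables 147, 154, 168 and 182, and to the serostatus versions where counts allow.

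The cost is a few words, one short definition and additional rows. The results are already collected by virus, so no samples or assays are added. The drawback is small or empty cells, which is why the subgroup tables can be left conditional. Attribution should be settled before anyone works through the listing with treatment assignments in view.
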